7.4 Derived Data

Change from pre to postoperative visits

This will be calculated as:

Post – operative value_{*visit* n} – Pre – operative value_(*Visit* 1) where n > 1.

CONFIDENTIAL AND PROPRIETARY

This document contains information that is confidential and proprietary to Smith & Nephew PLC and Smith & Nephew, Inc. and is intended for use only by Smith+Nephew and its manufacturer. It shall not be reproduced or copied in whole or in part, nor shall the contents be disclosed by any means without prior written permission from Smith+Nephew, nor shall anyone make any use of it that is contrary to the expressed or implied wishes of Smith+Nephew.

Statistical Analysis Plan

A Prospective, Multi-center, Randomized, Controlled Study to Evaluate theVersion: 2.0,Safety and Efficacy of the OR3O™ Dual Mobility System versus conventional29-Feb-2024single bearing design Total Hip System in Primary Total Hip Arthroplasty (THA)Page: 15 of 27ProceduresProcedures

Number: OR3O.2019.10 ST: 1100 Version: 2.0, 29-Feb-2024 Page: 15 of 27

Body Mass Index (BMI)

- BMI = {(Weight in kg)/(Height in m)²}, if units are in kg for weight and m for height
- BMI = {(Weight in lbs.)x703.07))/(Height in inches)²}, if units are in lbs. for weight and inches for height (Adjustments made to formula to standardize BMI unit to kg/m²)

Time to Revision

• Time to revision (in months) = (Revision Date – Operative Date + 1)/30.4375.

Hip disability and Osteoarthritis Outcome Score for Joint Replacement (HOOS JR)

The HOOS JR is a short-form survey based on the HOOS that specifically focuses on the outcome after THA. HOOS JR consists of the following 2 items:

- Pain (2 items) and
- Activities of daily living (4 items).

Each item (question) that is used for scoring the HOOS JR is rated on a scale of 0 to 4 as follows:

- \circ 0 = None; 1 = Mild; 2 = Moderate; 3 = Severe and; 4 = Extreme.
- The range of potential sum of raw scores for all 6 items of the HOOS JR is between 0 and 24 where 0 is the best score and 24 is the worst possible score. The maximum allowable number of missing items on the HOOS JR is 2. If more than 2 of the 6 items are missing, the raw HOOS JR score will not be computed. If 1 or 2 of the item scores are missing, the rounded average of the other non-missing items for that subject will be imputed. An interval score from 0-100 (0 indicating total hip disability and 100 indicating perfect hip health) is extrapolated from the sum of the HOOS JR item scores [1].

Five-level Euro QoL five-dimensional score (EQ-5D-5L)

The classification system of the EQ-5D-5L is comprised of five dimensions, namely mobility, selfcare, usual activities, pain/discomfort and anxiety/depression with each of the dimensions having five levels: "no problem" (level 1), "slight problems" (level 2), "moderate problems" (level 3),

CONFIDENTIAL AND PROPRIETARY

This document contains information that is confidential and proprietary to Smith & Nephew PLC and Smith & Nephew, Inc. and is intended for use only by Smith+Nephew and its manufacturer. It shall not be reproduced or copied in whole or in part, nor shall the contents be disclosed by any means without prior written permission from Smith+Nephew, nor shall anyone make any use of it that is contrary to the expressed or implied wishes of Smith+Nephew.

Statistical Analysis Plan

A Prospective, Multi-center, Randomized, Controlled Study to Evaluate theVersion: 2.0,Safety and Efficacy of the OR3O™ Dual Mobility System versus conventional29-Feb-2024single bearing design Total Hip System in Primary Total Hip Arthroplasty (THA)Page: 16 of 27ProceduresProcedures

Number: OR3O.2019.10 ST: 1100 Version: 2.0, 29-Feb-2024 Page: 16 of 27

"severe problems" (level 4), and "extreme problems" (level 5). Hence, the system defines 3125 (5⁵) health states ranging from 11111 to 55555 (i.e. the best possible health state to the worst possible health state).

 The individual domain responses on each of the 5 levels a scale of 1-5 will be combined based on the levels scored combining the domains to form a 5-digit number in the form XXXXX (where X is 1-5) describing the respondent's health state as previously described. The EQ-5D-5L index value would be derived by using the vendor supplied calculator in Microsoft Excel[®] to convert each 5digit EQ-5D-5L profile.

Harris Hip Score (HHS)

The HHS is a joint specific score that consists of 10 items covering domains of pain (1 item, 0-44 points), function (7 items, 0-47 points), absence of deformity (1 item, 0 or 4 points), and hip range of motion (2 items, 0-5 points). The overall HHS ranges from 0 (worst) to 100 (best).

Algorithms used for scoring each of the 10 items (components) of the HHS as well as its domains (pain, function, AoD and ROM) as well as total HHS are summarized in Table 3.

Table 3. Harris Hip Score (HHS) scores per item and domain				
	· · · · · · · · · · · · · · · · · · ·	-		
Item	Original Response	Likely scores per Item	Domains (Range of Scores)	
Pain	None or ignores it	44	Pain Domain (0 to 44)	
	Slight, minimal, no compromise in activities	40		
	Mild pain, no effect on average activities, rarely moderate pain with unusual activity; may take aspirin	30		
	Moderate pain; tolerable but makes concessions to pain. Some	20		

CONFIDENTIAL AND PROPRIETARY

This document contains information that is confidential and proprietary to Smith & Nephew PLC and Smith & Nephew, Inc. and is intended for use only by Smith+Nephew and its manufacturer. It shall not be reproduced or copied in whole or in part, nor shall the contents be disclosed by any means without prior written permission from Smith+Nephew, nor shall anyone make any use of it that is contrary to the expressed or implied wishes of Smith+Nephew.

TMP-CD-30-01 Statistical Analysis Plan – Revision B; SOP-CD-30 Statistical Analysis

Statistical Analysis Plan

A Prospective, Multi-center, Randomized, Controlled Study to Evaluate the
Safety and Efficacy of the OR3O[™] Dual Mobility System versus conventional
single bearing design Total Hip System in Primary Total Hip Arthroplasty (THA)Version: 2.0,
29-Feb-2024
Page: 17 of 27
Procedures

Number: OR3O.2019.10 ST: 1100 Version: 2.0, 29-Feb-2024 Page: 17 of 27

	limitation of ordinary activity or		
	work. May require occasional pain		
	medication stronger than aspirin	10	
	Marked pain, serious limitation of	10	
	activities	-	
	Totally disabled, crippled, pain in	0	
	bed, bedridden		
Limp	None	11	Function Domain (0
	Slight	8	to 47)
	Moderate	5	
	Severe	0	{Sum of all items
			within subdomain}
Support	None	11	
	Single cane for long walks	7	
	Single cane most of the time	5	
	One crutch	3	•
	Two canes	2	
	Two crutches or not able to walk	0	
		0	
Distance walked	Unlimited	11	
Distance walked	Six blocks	8	-
	Two or three blocks	5	
	Indoors only	2	
	Bod and chair only	0	
		0	
Sitting	Comfortably in ordinary chair	5	
Sitting	On a high chair for 30 minutos	3	
	Unable to sit comfortably in any	0	
	chair	0	
Public	Voc. possible	1	
transportation			
transportation	No unable	0	
		0	
Stairs	Normally without using a railing	4	-
Stans	Normally using a railing	2	-
	In any manner	1	
	Linable to do stairs	0	1
		0	4
Socks/Shoos	With ease	1	4
JUCKS/ JILLES	With difficulty	1 1	•
		2	4
	Unable	U	4

CONFIDENTIAL AND PROPRIETARY

Statistical Analysis Plan

A Prospective, Multi-center, Randomized, Controlled Study to Evaluate theVersion: 2.0,Safety and Efficacy of the OR3O™ Dual Mobility System versus conventional29-Feb-2024single bearing design Total Hip System in Primary Total Hip Arthroplasty (THA)Page: 18 of 27ProceduresProcedures

Range of Motion (ROM)	Flexion = FLEX+EXT-FLEX_ZERO	N/A			
	Movement = ABD+ADD- ABD_ZERO	N/A			
	Rotation = ER+IR-ER_ZERO	N/A			
ROM subscore	Flexion+Movement+Rotation		Range of Motion Domain (0 to 5))		
	0 to 29	0			
	30 to 59	1			
	60 to 99	2			
	100 to 159	3			
	160 to 209	4			
	≥ 209	5			
Leg Length Difference (in mm)	None	N/A			
	Ipsilateral longer (LL_DIF_LONG)	N/A			
	Ipsilateral shorter (LL_DIF_SHORT)	N/A			
Absence of Deformity (AOD)	IF (FLEX_ZERO = . OR FLEX_ZERO < 31) AND (ABD_ZERO = . OR ABD_ZERO < 11) AND (ER_ZERO = . OR ER_ZERO < 11) AND LL_DIF_LONG < 33 AND LL_DIF_SHORT < 33 THEN AODScore = 4	0 or 4	Absence of Deformity Domain (0 to 4)		
		Cum of all			
Iotal HHS		domain scores per subject	sum of all domain scores per subject		
Note: The maximum possible score for the HHS is 100.					

7.5 Baseline Data

Preoperative or operative variables will be summarized using descriptive characteristics for continuous¹ or categorical² data as applicable.

Number: OR30.2019.10 ST: 1100 Version: 2.0, 29-Feb-2024 Page: 18 of 27

CONFIDENTIAL AND PROPRIETARY

This document contains information that is confidential and proprietary to Smith & Nephew PLC and Smith & Nephew, Inc. and is intended for use only by Smith+Nephew and its manufacturer. It shall not be reproduced or copied in whole or in part, nor shall the contents be disclosed by any means without prior written permission from Smith+Nephew, nor shall anyone make any use of it that is contrary to the expressed or implied wishes of Smith+Nephew.

Statistical Analysis Plan

A Prospective, Multi-center, Randomized, Controlled Study to Evaluate the Version: 2.0, Safety and Efficacy of the OR3O[™] Dual Mobility System versus conventional single bearing design Total Hip System in Primary Total Hip Arthroplasty (THA) Page: 19 of 27 Procedures

- Age¹ (in years),
- Sex² (males or females),
- Bilateral status (i.e. unilateral or bilateral)²,
- Body Mass Index (BMI)¹,
- Primary hip diagnosis²,
- Charnley Co-morbidity Classification²,
- Components of the device implanted².
- Surgical approach used².
- \circ Side of implantation (left versus right versus both left and right) ².

Variables summarized will not only be restricted to the above listed but on all variables deemed pertinent and obtainable preoperatively and operatively.

Additionally, age will be categorically summarized by stratifying into: < 60 years versus \geq 60 years. BMI will also be categorically summarized by stratifying into: < 30 kg/m² versus \geq 30 kg/m².

CONFIDENTIAL AND PROPRIETARY

Number: OR3O.2019.10 ST: 1100 Version: 2.0, 29-Feb-2024 Page: 19 of 27

This document contains information that is confidential and proprietary to Smith & Nephew PLC and Smith & Nephew, Inc. and is intended for use only by Smith+Nephew and its manufacturer. It shall not be reproduced or copied in whole or in part, nor shall the contents be disclosed by any means without prior written permission from Smith+Nephew, nor shall anyone make any use of it that is contrary to the expressed or implied wishes of Smith+Nephew.

Statistical Analysis Plan

A Prospective, Multi-center, Randomized, Controlled Study to Evaluate theVersion: 2.0,Safety and Efficacy of the OR3O™ Dual Mobility System versus conventional29-Feb-2024single bearing design Total Hip System in Primary Total Hip Arthroplasty (THA)Page: 20 of 27ProceduresProcedures

Number: OR3O.2019.10 ST: 1100 Version: 2.0, 29-Feb-2024 Page: 20 of 27

7.6 Disposition Data

- Subject (and hip) disposition will be summarized after completion of the study using frequency (n) and percentage (%) of subjects (or hips) who completed and who did not complete the study. For those who did not complete the study, the primary reason for discontinuation will additionally be summarized. A listing of subject (and hip) disposition at both interim and at termination visits will be provided.
- Hip accountability information will be tabulated by visit. The information included in this table will include the number of hips that are theoretically due, subjects who are dead, hips revised, hips terminated from the study for any reason. Additional information that will be included on the subject accountability table will include but not limited to the number of hips presenting at each visit, number of hips expected at each visit.

7.7 Protocol Deviations

A listing of deviations encountered on-study will be listed. Major protocol deviations that are deemed significant which will subsequently lead to the exclusion of subjects in the PP population will be appropriately identified and flagged.

7.8 Measurement of Treatment Compliance

Not applicable.

7.9 Multiplicity

The null hypothesis will be rejected for Ha1/Ha2 if the lower bound of the 2-sided 95% CI of p1-p0 is above the respective margin (ie, $-\Delta$ or 0), respectively or both using a stepwise hypothesis

CONFIDENTIAL AND PROPRIETARY

This document contains information that is confidential and proprietary to Smith & Nephew PLC and Smith & Nephew, Inc. and is intended for use only by Smith+Nephew and its manufacturer. It shall not be reproduced or copied in whole or in part, nor shall the contents be disclosed by any means without prior written permission from Smith+Nephew, nor shall anyone make any use of it that is contrary to the expressed or implied wishes of Smith+Nephew.

Statistical Analysis Plan

A Prospective, Multi-center, Randomized, Controlled Study to Evaluate the
Safety and Efficacy of the OR3O[™] Dual Mobility System versus conventional
single bearing design Total Hip System in Primary Total Hip Arthroplasty (THA)Version: 2.0,
29-Feb-2024
Page: 21 of 27ProceduresProcedures

Number: OR30.2019.10 ST: 1100 Version: 2.0, 29-Feb-2024 Page: 21 of 27

testing approach. This stepwise hypothesis-testing framework would not require any adjustment made to a, thus strongly controlling the overall significance at 0.05.

7.10 Analysis of Primary Endpoint

The analysis of the primary endpoint will utilize hypothesis testing in two steps. First, testing for non-inferiority of P1 versus P0 and secondly if non-inferiority is demonstrated then testing for superiority of P1 to P0 as follows:

H0 (null): P1 \leq (P0- Δ) versus Ha1 (alternate 1st stage): P1 > (P0- Δ) and Ha2 (alternate 2nd stage): P1 > P0,

Where Δ is the margin of non-inferiority (9.5%), P1 is the proportion of good to excellent HHS scores at 12 months in the OR3O dual mobility system (test) and P0 is the proportion of good to excellent HHS scores at 12 months in the Conventional, single-bearing design (control).

- The null hypothesis, H0, is rejected in favor of the first alternate hypothesis, Ha1, (i.e. demonstration of non-inferiority) if the lower limit of the 95% Confidence interval for P1p0 > $-\Delta$) otherwise, H0 will be accepted.
- If the null hypothesis, H0, is rejected and in favor of Ha1, the test for superiority would be performed. If the upper limit of the 95% CI for P0 is less than the lower limit of the 95% CI for P1, then superiority of P1 to P0 is demonstrated, i.e. acceptance of Ha2.. This stepwise hypothesis-testing framework would not require any adjustment made to a, thus strongly controlling the overall significance at 0.05. All 95% CIs generated for P1 and P0 would be calculated using exact methods.

However, as this study has been early terminated the study no longer has sufficient power for this test to be relevant and it will therefore not be performed. Summary statistics for P1 and P0 will be reported.

The primary endpoint will be summarized using the SAF population.

CONFIDENTIAL AND PROPRIETARY

This document contains information that is confidential and proprietary to Smith & Nephew PLC and Smith & Nephew, Inc. and is intended for use only by Smith+Nephew and its manufacturer. It shall not be reproduced or copied in whole or in part, nor shall the contents be disclosed by any means without prior written permission from Smith+Nephew, nor shall anyone make any use of it that is contrary to the expressed or implied wishes of Smith+Nephew.

Statistical Analysis Plan

A Prospective, Multi-center, Randomized, Controlled Study to Evaluate the
Safety and Efficacy of the OR3O™ Dual Mobility System versus conventional
single bearing design Total Hip System in Primary Total Hip Arthroplasty (THA)Version: 2.0,
29-Feb-2024
Page: 22 of 27ProceduresPage: 22 of 27

Number: OR3O.2019.10 ST: 1100 Version: 2.0, 29-Feb-2024 Page: 22 of 27

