10.2 ANALYSIS POPULATIONS

The following section details the analysis populations:

- Safety (SAF) Population: This is defined as all hips who have been implanted with the OR3O™ Dual Mobility System or controlled system.

CONFIDENTIAL AND PROPRIETARY

This document contains information that is confidential and proprietary to Smith & Nephew PLC and Smith & Nephew, Inc. and is intended for use only by Smith & Nephew and its manufacturer. It shall not be reproduced or copied in whole or in part, nor shall the contents be disclosed by any means without prior written permission from Smith & Nephew, nor shall anyone make any use of it that is contrary to the expressed or implied wishes of Smith & Nephew.

Clinical Protocol	Study Number: OR3O.2019.10 (China)
Prospective, Multi-center, Randomized, Controlled Study to Evaluate the Safety and Efficacy of the OR3O™ Dual Mobility System versus conventional single bearing design Total Hip System in Primary Total Hip Arthroplasty (THA) Procedures	Version: 1.0, 18Aug2020
	Page: 53 of 90

- Full Analysis Set (FAS) Population: according to the basic principle of Intent-to-Treat (ITT) analysis, all randomly selected subjects with at least one validity evaluation will be included in FAS Population.
- Per-Protocol (PP) Population: The PP population is a subset of hips in the FAS population who do not have major protocol deviations and who satisfied all enrollment eligibility criteria. Criteria that can be regarded as major deviations will be formally classified on a case-by-case basis prior to the final study database lock.

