10.4 EFFICACY ANALYSIS

10.4.1 Analysis of Primary Endpoint

The primary endpoint of this study is the proportion of excellent (≥ 90) or good (80-89) HHS scores at 12 month postoperative. Hypothesis testing would be in two steps. First, testing for non-inferiority of P1 versus P0 and secondly if non-inferiority is demonstrated then testing for superiority of P1 to P0 as follows:

H0 (null): $P1 \leq (P0 - \Delta)$ versus

Ha1 (alternate 1st stage): $P1 > (P0 - \Delta)$ and Ha2 (alternate 2nd stage): $P1 > P0$,

Where Δ is the margin of non-inferiority (9.5%), P1 is the proportion of good to excellent HHS scores at 12 months in the OR3O dual mobility system (test) and P0 is the proportion of good to excellent HHS scores at 12 months in the Conventional, single-bearing design (control).

- The null hypothesis, H0, is rejected in favor of the first alternate hypothesis, Ha1, (i.e. demonstration of non-inferiority) if the lower limit of the 95% Confidence interval for $P1 > (P1 - \Delta)$ otherwise, H0 will be accepted.
- If the null hypothesis, H0, is rejected in favor of Ha1, the test for superiority would additionally be performed. If the upper limit of the 95% CI for P0 is less than the lower limit of the 95% CI for P1, then superiority of P1 to P0 is demonstrated, i.e. acceptance of Ha2.. This stepwise hypothesis-testing framework would not require any adjustment made to α , thus strongly controlling the overall significance at 0.05. All 95% CIs generated for P1 and P0 would be calculated using exact methods.

The primary endpoint will be summarized using the ITT population as the primary analysis population and then subsequently with the per PP population for sensitivity analysis.

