7 STATISTICAL ANALYSIS

The Full Analysis Set (FAS) population will be used to summarize the primary and all secondary endpoints (excluding radiographic assessments) while the Safety (SAF) population will be used summarize all safety and exploratory endpoints. The SAF population will additionally be used to summarize radiographic assessments The Per Protocol (PP) population will additionally be used to summarize the primary endpoint.

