7.2 Analysis Populations

The following section details the analysis populations:

TMP-CD-30-01 Statistical Analysis Plan - Revision B; SOP-CD-30 Statistical Analysis

CONFIDENTIAL AND PROPRIETARY

This document contains information that is confidential and proprietary to Smith & Nephew PLC and Smith & Nephew, Inc. and is intended for use only by Smith+Nephew and its manufacturer. It shall not be reproduced or copied in whole or in part, nor shall the contents be disclosed by any means without prior written permission from Smith+Nephew, nor shall anyone make any use of it that is contrary to the expressed or implied wishes of Smith+Nephew.

Statistical Analysis Plan

A Prospective, Multi-center, Randomized, Controlled Study to Evaluate theVersion: 2.0,Safety and Efficacy of the OR3O[™] Dual Mobility System versus conventional29-Feb-2024single bearing design Total Hip System in Primary Total Hip Arthroplasty (THA)Page: 13 of 27ProceduresProcedures

Number: OR3O.2019.10 ST: 1100 Version: 2.0, 29-Feb-2024 Page: 13 of 27

Safety (SAF) Population: This is defined as all hips who have been implanted with the OR3O[™] Dual Mobility System or controlled system. The SAF population will be based on the device that is implanted into the hip and not the one the hip is randomized to (if different).

Full Analysis Set (FAS) Population: This is defined according to the basic principle of Intent-to-Treat (ITT) principle i.e., all implanted hips with at least one postoperative effectiveness, HRQoL or performance will be included in FAS Population.

Per-Protocol (PP) Population: The PP population is the subset of hips in the FAS population who do not have major protocol deviations and who satisfied all enrollment eligibility criteria. Criteria that can be regarded as major deviations will be formally classified on a case-by-case basis prior to the final study database lock.

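### SAP v2.0 names conflicting populations for the primary endpoint, and in cancelling the primary test it also drops any commitment to report P1−P0 with a confidence interval

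*SAP*

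**What the plan says.** **Population.** SAP section 7 states: "The Full Analysis Set (FAS) population will be used to summarize the primary and all secondary endpoints" (radiographic assessments excepted), and "The Per Protocol (PP) population will additionally be used to summarize the primary endpoint". Protocol 10.4.1 agrees in substance: "The primary endpoint will be summarized using the ITT population as the primary analysis population", followed by PP as sensitivity. SAP 7.10 ends differently: "The primary endpoint will be summarized using the SAF population". SAP 7.11 makes the same move to the SAF for all secondary endpoints. Under SAP 7.2 the SAF is "based on the device that is implanted into the hip and not the one the hip is randomized to".

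**Definition of the FAS.** Protocol 10.2 has "all randomly selected subjects with at least one validity evaluation will be included in FAS Population". SAP 7.2 narrows this to "all implanted hips with at least one postoperative effectiveness, HRQoL or performance will be included in FAS Population". It invokes the ITT principle but does not say outright that hips are grouped as randomised.

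**Contrast.** SAP 7.10 cancels the non-inferiority and superiority steps for lack of power and continues: "it will therefore not be performed. Summary statistics for P1 and P0 will be reported". SAP 7.9 still bases rejection of the null hypothesis on the two-sided 95% CI of p1−p0 and is not marked as withdrawn. SAP 7.15 records that tests are replaced by descriptive summaries. It mentions neither the population nor an interval for the difference.

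**Missing 12-month scores.** SAP 7.3 carries the last postoperative value forward, and counts a hip with no postoperative value as a failure.

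**The concern.** Two operative sentences of the same SAP, in section 7 and in 7.10, cannot both be followed for the main table. They can give different groupings (if any hip received a device other than the one allocated) and different denominators (if any implanted hip was never assessed after surgery). The change log does not tell the reader which was intended, or why.

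The between-arm estimate also goes out with the test. Protocol 4.3 gives comparison of the two systems as the study's purpose, and protocol 11.6 judges the result on the CI of the difference. Lack of power is a sound reason to draw no non-inferiority or superiority conclusion. It is not a reason to leave out the estimated difference and its precision, which show how large a deficit of the new device the data leave open. At stake is a clear report of the randomised comparison in one defined population.

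**Working it through.** **1. The populations side by side.**

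| Place | Set for the primary endpoint |
|---|---|
| Protocol 10.4.1 | ITT, then PP |
| SAP section 7 | FAS, plus PP |
| SAP 7.10 | SAF |
| SAP 7.15 (changes) | not mentioned |

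The SAF holds all implanted hips by device received. The SAP's FAS holds implanted hips with at least one postoperative assessment. Neither contains subjects randomised but not implanted, whom protocol 7.6 and 7.8.1 treat as screen failures, so neither gives a full all-randomised contrast.

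**2. Effect on the denominator without crossover (assumed counts).** Suppose one arm has 38 successes among 40 hips in the FAS, and four further implanted hips were never assessed after surgery. Under SAP 7.3 those four are failures in the SAF. FAS: 38/40 = 95.0%. SAF: 38/44 = 86.4%. The shift is 8.6 points, against a margin of 9.5. If both arms lost hips equally the contrast would barely move; if only one did, it would move by the full amount.

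**3. The plan's own figures.** Margin: 0.95 − 0.90 × 0.95 = 0.095. Enrolment: 76/0.90 = 84.4, so 85 per arm. The 76 is reached with a score test at one-sided 0.05 (exact power 80.1%), and within one subject by a ratio-margin formula at one-sided 0.025 (75). The usual difference formula at one-sided 0.025 gives (1.960 + 0.842)² × 2 × 0.95 × 0.05 / 0.095² = 82.6, so 83. That is a separate question and does not affect this point.

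**4. Precision of P1−P0.** The achieved number is not in the documents, so sizes and rates are assumed, with equal counts in both arms. For observed proportion p with Wilson limits l and u in each arm, the Newcombe half-width is √[(p − l)² + (u − p)²].

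- 38/40: l = 83.50%, u = 98.62%; √(11.50² + 3.62²) = 12.1 points.
- 34/40: l = 70.93%, u = 92.94%; √(14.07² + 7.94²) = 16.2 points.

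Half-widths in points, Newcombe / Miettinen–Nurminen:

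| Per arm | about 95% | about 90% | about 85% |
|---|---|---|---|
| 20 | 19.1 / 19.7 | 21.4 / 22.3 | 23.2 / 24.3 |
| 40 | 12.1 / 12.3 | 14.4 / 14.7 | 16.2 / 16.6 |
| 60 | 9.3 / 9.4 | 11.5 / 11.7 | 13.1 / 13.3 |
| 76 (planned) | 8.2 / 8.3 | 10.2 / 10.4 | 11.4 / 11.6 |

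Smaller numbers or lower success widen it further: 10/10 per arm gives ±27.8 (Newcombe), and 28/40 gives ±19.5. With fully observed outcomes, enumerated Newcombe coverage was 95.2% to 99.8% for 20 to 76 per arm and true test/control rates of 95/95, 90/95, 90/90 and 85/95. Imputed values are outside that check.

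**5. Separate exact intervals do not replace it.** At 38/40 per arm, each Clopper–Pearson interval is 83.1% to 99.4%. Subtracting opposite limits gives ±(99.4 − 83.1) = ±16.3 points, against ±12.1 for the difference itself.

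**The case against.** The strongest reply is that little information is lost. SAP 7.1 promises n and % for categorical variables, so a reader with the per-arm counts can compute the difference and a score interval. The CI criterion in protocol 11.6 belongs to the completed trial and is not a reporting duty after termination. HHS shift tables (7.11), hip accountability (7.6) and the deviation listing (7.7) help further. This stands in part: the request for an interval concerns clear reporting. It does not meet the population conflict, because the reader would not know which set the counts come from or how many values were imputed.

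A second reply is that the FAS is not simply better. It removes implanted hips never assessed after surgery, which the SAF would retain and SAP 7.3 would count as failures. This stands. The choice trades randomised grouping against retention, and keeping the SAF with a stated reason would also remove the contradiction.

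A third is that an interval on carried-forward data treats scores from as early as 6 weeks as 12-month outcomes. This stands too, so the observed-case result belongs beside it.

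A reader might infer that the SAP nowhere mentions an interval for the difference. SAP 7.9 does; the fair reading is that 7.10 and 7.15 override it. A reader might also infer that the as-implanted grouping has altered the result. The documents do not say whether any hip received a device other than the one allocated.

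**Conclusion.** The population contradiction is established from the text: section 7 of the SAP and protocol 10.4.1 point one way, SAP 7.10 and 7.11 the other, and 7.15 is silent. It is also established that SAP v2.0, read with its overrides, leaves no commitment to report P1−P0 with a CI.

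The point should be acted on, but its weight is limited. No efficacy claim rests on it, and nothing here supports reinstating the test: at about 95% success, a zero observed difference already has a Newcombe lower limit of −9.9 points at 48/50 per arm, beyond the 9.5-point margin. The precision figures are an assumed range and do not predict the achieved interval. If no hip crossed over and every implanted hip was assessed after surgery, SAF and FAS would coincide and only the missing contrast and the unlisted change would remain.

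**What to change.** (a) In SAP 7.10, report P1−P0 with a two-sided 95% score-type CI (Newcombe or Miettinen–Nurminen), grouped as randomised. Label it as estimation after early termination, with no non-inferiority or superiority claim. Mark the decision rules in 7.9 and 7.10 as not applied.

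(b) Make 7.10 and 7.11 agree with section 7: FAS for the primary and secondary endpoints, plus PP for the primary, with radiographic assessments staying in the SAF. An as-implanted SAF summary may stay as supportive. If the SAF is kept as the main set, list the change and its reason in 7.15.

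(c) Show the result in hips with an observed 12-month HHS beside the LOCF result. Per arm, give the numbers observed at 12 months, carried forward and set to failure, the number implanted but outside the FAS for lack of any postoperative assessment, and the number randomised but not implanted. Note that the FAS is not an all-randomised set.

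**Cost.** A few table rows, one count table and SAP wording; no new data. The interval will be wide and will not reflect uncertainty from carried-forward values. Choosing the FAS leaves out implanted hips never assessed after surgery, so their number must be visible.
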